6.3.3.10 Subject Post Treatment Assessments

PDC will capture subject reported local and systemic events for 7 days after the study treatment as shown in Appendix A.

The subject will be provided a PDC and will be asked to record the following the evening of study treatment through Day 6:

- Oral temperature and time taken (before 11:59 pm)
- General symptoms of feeling unwell
- Pain and itching at injection site
- Measure redness, swelling, bruising at injection site
- Medications taken

The completed PDC will be reviewed with the subject and research staff at 8 -14 Days post-dose.

The study staff will review the PDC for general symptoms (e.g. malaise, fatigue, headache, nausea, and myalgia/arthralgia), injection site reaction symptoms (e.g. pain, erythema and edema), medical events and medications. All reported events will be assessed for clinical significance (CS) and reported as adverse event accordingly.

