6.7 ASSESSMENT OF INJECTION SITE REACTIONS

When evaluating injection site reactions throughout the study, the investigator will be instructed to use the following grading scale:

Table 12. Grading Scale for Injection Site Reactions

Local Reaction to Injectable Product (Grade)	Mild(1)	Moderate(2)	Severe(3)	Potentially Life Threatening(4)
Pain	Does not interfere with activity	Repeated use of non- narcotic pain reliever >24 hours or interferes with activity	Any use of narcotic pain reliever or prevents daily activity	Emergency room (ER) visit or hospitalization
Tenderness	Mild discomfort to touch	Discomfort with movement	Significant discomfort at rest	ER visit or hospitalization
Erythema/Redness*	2.5-5 cm	5.1-10 cm	>10 cm	Necrosis or exfoliative dermatitis
Induration/Swelling**	2.5-5 cm and does not interfere with activity	5.1-10 cm or interferes with activity	>10 cm or prevents daily activity	Necrosis

⁻ September 2007 "FDA Guidance for Industry—Toxicity Grading Scale for Healthy Adult and Adolescent Volunteers Enrolled in Preventive Vaccine Clinical Trials"

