7.3.1 EVENTS REQUIRING EXPEDITED REPORTING

Events requiring expedited reporting (ERER) will be defined as related adverse events due to VGX-3100X/placebo delivered with CELLECTRA[™] 5PSP that meets any of the following criteria:

- Grade 3 or greater administration site erythema, and/or induration recorded ≥ 2 hours after Study Treatment
- Grade 4 or greater administration site pain, tenderness recorded ≥ 2 hours after Study Treatment
- Grade 3 or greater fever
- Grade 3 or greater systemic symptoms, including generalized pruritus

As per the Toxicity Grade for Healthy Adults and per CTCAE v 4.03. The most severe grade for that particular event is to be documented in the CRFs.

Sites will inform the Sponsor vial email and to designee vial phone or fax of any ERER within 24 hours to discuss whether further dosing should continue by contacting Inovio as follows.

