9.5.1 STUDY REPORTING PERIOD OF ADVERSE EVENTS

All solicited and unsolicited adverse events will be collected throughout the study and recorded on the AE CRF. Safety events will be analyzed and summarized throughout the study. Emphasis will be placed on the following:

- Certain AEs of interest will be solicited during the 7 days following each administration of Study Treatment and summarized separately
- Unsolicited AEs, SAEs or UADEs will be collected and summarized for the entire study period

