15 APPENDICES

15.1 APPENDIX A: PARTICIPANT DIARY CARD

Subject Diary

HPV-301

Subject #: _	
Injection Da	ate:

Note to Participant:For questions or problems, please contact your Site Coordinator.

Name:	
Telephone: ()
Email (optional):	

Participant Diary HPV-301 Version 1.0 - 10 May 2016

Temperature

Take your temperature orally around the same time each evening, using the thermometer provided and record it in the space provided. Also record the time at which you took your temperature. If you recently drank very hot or cold liquids, wait 15 minutes before taking your temperature.

Injection Site Symptoms

Pain and itching

Some people experience pain in the area where they were injected. Some people may also experience itching in the area where they were injected.

• By pain we mean that the place where you were injected hurts even when it isn't touched.

If you experience pain or itching at the injection site, use the following categories to describe how severe these symptoms were. If you don't experience one or more of these symptoms, mark the **NONE** box.

- Mild in I only had a little discomfort. I could still use my arm like always.
- Moderate . I noticed the discomfort and didn't use my arm as much as usual.
- Severe I really noticed the discomfort. It kept me from doing something I wanted or had to do.

Redness, swelling, and bruising

Some people experience redness, swelling, or bruising in the area where they were injected. If you experience redness, swelling, or bruising, measure the area using the measuring tool you were provided, and record the measurement in the space provided.

To measure the area of redness, swelling, or bruising, do the following:

- Place the measuring tool over the area where you were injected, with the dot over the center of the area.
- Select the circle where the longest part of the area touches the line.
- If the area is in between two circles, select the larger circle.

For example, the area shown to the right measures 3 centimeters (cm) because it is touching the 3cm line.

General and Other Symptoms or Medications

If you have additional symptoms that are not listed, or if you sought medical care for any reason from a health care provider (e.g. doctor's office, emergency room), or if you took any medications, these should be listed in the spaces provided. Please designate any symptoms as Mild, Moderate, or Severe.

- Mild I only had minor discomfort. I went about my usual activities.

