2.3 SAFETY MONITORING PLAN

Although cervical HSIL is thought to require years to progress to cervical cancer, subjects in the Phase 2b study were followed closely throughout. HPV testing (Weeks 14 and 24), cytology (Week 14) and colposcopy (Week 24) were all mandatory during the observation period prior to obtaining tissue for determination of the primary histologic endpoint at Week 36. Investigators were also instructed to perform additional testing (including biopsy) if disease progression was suspected. These instances were infrequent as only 11 unscheduled biopsies were deemed necessary over the course of the Phase 2b study. In addition, the rate at which occult microinvasive cancer was discovered after 36 weeks was less frequent than what is reported in the literature [22]. Both observations would imply that the mandatory monitoring employed in the Phase 2b study was sufficient; however cervical disease will be monitored even more closely in this Phase 3 study. Colposcopy, cytology and HPV testing will be required at 8 to 14 week intervals throughout the observation period leading up to the primary endpoint 36 weeks after the first dose. Although less frequent monitoring may be adequate, the more frequent monitoring is designed to afford an even wider margin of safety and an opportunity to explore predictors of efficacy.

Safety monitoring will include:

- Local and systemic events for 7 days following each treatment as noted on a Participant Diary Card (PDC).
- All adverse events including SAEs, UADEs, and other unexpected AEs for the duration of the study;

In the Phase 2b study, the safety profile was carefully evaluated and treatment with VGX-3100 was well-tolerated based on observations through Week 88 in all subjects. The most common adverse events were administration-site reactions, which included pain, tenderness, erythema and swelling, and were generally mild and limited to a few days in duration. Only erythema showed a statistically higher incidence in VGX-3100 (78%) vs. placebo (57%) in the 7- and 28-day periods after a dose. One additional AE, sinusitis, was also statistically significantly increased over the course of the entire study period but resolved without sequelae in the VGX-3100 arm compared to the Placebo arm (10% vs. 0%).

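### The participant diary shown has no daily item for tenderness, and its definition of pain keeps touch-only discomfort out of the pain item

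*Protocol*

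**What the plan says.** Section 6.3.3.10 makes the diary the instrument for the first week: "PDC will capture subject reported local and systemic events for 7 days after the study treatment". Its list of local items is "Pain and itching at injection site" and "Measure redness, swelling, bruising at injection site". The diary pages for Days 0 to 6 in Appendix A carry the same five items. Pain and itching have severity boxes, and the other three are measured in centimetres. The instructions define pain: "By pain we mean that the place where you were injected hurts even when it", continuing that this is so without touch. Symptoms not on the list go into a free-text block.

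Section 9.5.1 of the same version adds: "Certain AEs of interest will be solicited during the 7 days following each administration of Study Treatment and summarized separately".

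Table 12 in section 6.7 gives investigators four graded local reactions: pain, tenderness, erythema/redness and induration/swelling. Grade 1 tenderness is "Mild discomfort to touch". Section 7.3.1 of that version uses tenderness in one of its criteria, "Grade 4 or greater administration site pain, tenderness recorded" at 2 hours or more after treatment. Section 2.3, kept in version 3.0, describes the most common Phase 2b adverse events as administration-site reactions, "which included pain, tenderness, erythema and swelling".

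**The concern.** Secondary endpoint 1a is the incidence and severity of local and systemic events over 7 and 28 days after each dose and over the whole study. For local reactions, the first week is when a daily prompted record matters most. The protocol treats tenderness as distinct from pain, both in its grading scale and in its account of Phase 2b. The form the woman fills in each evening has no place for it, and the pain definition tells her not to enter it under pain. A woman who follows the form exactly, and whose arm hurts only when pressed, marks no pain and is asked nothing further about it.

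At stake is the completeness of one commonly expected reaction in the 7-day safety tables, and the reliability of its grade.

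**Working it through.** No arithmetic tests this point. The check sets the items side by side.

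**Table 12 reactions against the diary (Days 0 to 6) and section 6.3.3.10**

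| Table 12 reaction | Prompted daily item |
|---|---|
| Pain | Yes, severity boxes |
| Tenderness | None |
| Erythema/redness | Yes, measured |
| Induration/swelling | Yes (swelling), measured |

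Three of the four graded reactions are prompted. The diary also prompts for itching and bruising, which Table 12 does not grade.

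**Could tenderness be entered as pain?** This depends on the Table 12 grade.
- Grade 1 is discomfort on touch. The diary's definition plainly excludes it.
- Grade 2 is discomfort on movement. The definition does not mention movement, so women may enter it differently.
- Grade 3 is significant discomfort at rest. The pain item could catch it.
- Grade 4 is an emergency room visit or hospitalization. The diary asks about medical care sought and names the emergency room as an example.

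The gap therefore lies in Grades 1 and 2.

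**Other routes to the record**
- Staff assess the site before and about 30 minutes after each dose (sections 6.2 and 6.6). This cannot show tenderness that develops later.
- The diary's free-text block for other symptoms is open but does not prompt for tenderness.
- The contact 8 to 14 days after each dose is by telephone (section 6.2). It includes diary review and a separate injection-site evaluation. Nobody can press the site, and the diary under review has no tenderness entry. The examples of injection-site symptoms that section 6.3.3.10 gives for staff review do not include tenderness.
- Later in-person assessments rely on recall for anything already resolved.

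**Effect on the tables.** Section 8.11.1 of the same version leaves events with a missing or partial onset date out of the day-range summaries. Tenderness recalled at the call without an exact date would count in the overall table but not in the 7-day or 14-day summaries.

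**Extent.** Each dose has 7 diary days, so three doses give 3 × 7 = 21 diary pages per woman without the item. The version to which this diary belongs plans 165 women, so up to 165 × 3 = 495 seven-day diaries are concerned. How many reports would be lost cannot be derived, because no separate tenderness rate is given.

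**The case against.** The strongest objection is that the diary shown is not the current one. Version 3.0 still lists a participant diary card in its contents, but the text available ends before that appendix. A reader might infer from the version 3.0 list of significant changes, which names no diary change, that the gap persists. That inference is weak, because other changes also went unlisted. Secondary endpoint 6 was reworded to progression to cervical carcinoma, and the contents show the colposcopy guideline directly after the diary, where the device error form used to stand. The point therefore holds only for the diary shown.

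The second objection is that tenderness is evaluated. Section 6.7 tells investigators to use Table 12 throughout the study, and site reactions are assessed about 30 minutes after dosing, at the 8 to 14 day call and at later visits. This stands: it would be wrong to say that tenderness is not collected. What is missing is the prompted daily self-report.

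Third, section 9.5.1 promises only that certain events are solicited. It does not say that every Table 12 reaction has a diary row. That is correct, so this is a gap between two instruments and not a broken promise.

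Three stronger readings are tempting and unsupported:
- *Expedited reporting is compromised.* It is barely exposed, since Grade 4 tenderness is defined by emergency or hospital care, which the diary does ask about. Section 7.3.1 was also modified in version 3.0, and the new text is not shown.
- *The rate will not be comparable with Phase 2b.* The protocol does not say how Phase 2b collected tenderness, so this cannot be judged either way.
- *Table 11 lists tenderness by itself as very common.* It lists pain or tenderness jointly. The support for tenderness as a separately named common event is section 2.3.

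**Conclusion.** The point stands as a minor, easily corrected gap in the form. In the diary shown and in section 6.3.3.10, tenderness is the only Table 12 reaction without a daily prompt, and the wording on pain shuts out touch-only discomfort. Mild to moderate tenderness arising after the 30-minute check is likely to be under-recorded in both arms in the 7-day part of secondary endpoint 1a.

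This rests on two assumptions: that women follow the diary's definition as written, and that an unprompted symptom is reported less completely than a prompted one. The amount cannot be quantified from the protocol. The primary endpoint and the efficacy analyses are not touched. If the version 3.0 diary already has a tenderness item, the point is closed.

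**What to change.** First check the version 3.0 diary. If it has no such item, add a row to each diary day reading *Tenderness (hurts when touched or moved)*, with the existing None/Mild/Moderate/Severe boxes, and list tenderness with pain and itching in section 6.3.3.10. No visit or procedure changes.

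The cost is a diary revision, its translation and notification of ethics committees. Women already dosed would remain on the old form, so the safety report should state which diary version each woman used when it presents tenderness.

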6.4 INJECTION AND ELECTROPORATION (EP)

Subjects will receive a 3-dose series of either 1 ml VGX-3100X or Placebo by IM injection in the deltoid (or anterolateral quadriceps muscle as an alternate option, if deltoid muscle is not possible or appropriate) followed immediately by EP with the CELLECTRA[™] 5PSP. Study treatment must not be given within 2 cm of a tattoo, keloid or hypertrophic scar. If there is implanted metal, implanted device, within the same limb then use of the deltoid muscle on the same side of the body is excluded.

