15.2 APPENDIX B: ERROR REPORTING FORM

Please complete the form	and fax to (267) 440	0-4242 or s	can the form to				
Protocol# Si	te# Subje	ct ID	Week#	Visit Date			
DEVICE INFORMATION							
CELLECTRA® 5PSP Base							
Located on label on the front cove CELLECTRA® 5PSP Hands		$\overline{}$					
Located on label on the handle	et Seliai NO []						
CELLECTRA® 5PSP Array		$\Box\Box\Box$					
Located on label on the package							
Time of Treatment:		and Locati ht Arm □I	on of Treatment:	: 🗆 IM 🗆 ID			
			. eπ Ann s □ R ight Quadri	icana			
			s Bright Quadin n, specify:	•			
IM-5P ONLY, was the EP (i, specify.				
If EP Guide was used, plea			ibiect's BMI				
II El Calde was asea, piea	se provide reason an	a il lolade o	abjects bivii.				
		_					
Was injection successful		(1978)	□ NO				
If NO, please provide reaso	n and include needle	gauge and	syringe volume u	sea.			
Did the diaples on the des	ios road ED avessa	ofulo 🗆 V	TC	□NO			
If NO, please check all com							
☐ Impedance Test Error m							
☐ Electroporation Error me							
☐ EP aborted by trigger or							
☐ Battery level too low for							
☐ Difficulty inserting array i		5 ,					
☐ Other, please specify below							
Describe device complication below (continue on back if necessary):							
Total # of arrays woods		T	-1 # -f -H				
Total # of arrays used:		10	al # of attempts:				
Impedance Test Error (IM							
Was the array fully inserted	in subject's arm?	☐ YES	□ NO				
(or thigh as applicable) Were all attempts performe	Over the same day?						
Was a different location use		☐ YES					
Was a new array used for e		☐ YES					
Please provide any additi			The second secon	cessany.			
r rease provide any additi		ion (contin	ac on back if fice	3035di y).			
Electroporation Error							
Were there 3 (IM) or 4 (ID)				NO (how many			
Was the array fully inserted	in the subject's arm?	?	☐ YES ☐ N	10			
Was the array inserted perp	the same and the s						
Did the needles of the array	appear damaged in	any way?	☐ YES ☐ N	10			
If you were provided a shar	ps shuttle, please eje	ct the array	into a shuttle and	ship to Inovio.			
Please provide any additi							
- 00							

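### The diary's Mild and Moderate anchors for injection-site pain and itching refer only to the arm although thigh injection is permitted, so intermediate thigh reactions have no applicable box and may be under-graded

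*Protocol*

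**What the plan says.** Appendix A gives three severity anchors for injection-site pain and itching and repeats its instructions for each of the seven diary days (Day 0 to Day 6):

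- The lowest box, Mild, pairs slight discomfort with an unaffected arm: "I only had a little discomfort. I could still use my arm like always".
- The middle box, Moderate, pairs awareness of the reaction with an arm that is used less: "I noticed the discomfort and didn't use my arm as much as usual".
- The highest box, Severe, turns on an activity that was prevented: "It kept me from doing something I wanted or had to do".

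The definition of pain on the same page is not tied to a limb: "By pain we mean that the place where you were injected hurts even when it isn't touched".

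On the injection site, Section 6.4 names the deltoid, with the "anterolateral quadriceps muscle as an alternate option, if deltoid muscle is not possible or appropriate". Version 3.0 keeps the rule: Section 5.9 uses the same words, and Section 2.2 calls the deltoid the preferred site and the quadriceps the alternate. The exclusion criterion on injection sites counts both muscles towards the two acceptable sites required, so a woman with thigh sites only is not excluded by it.

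On grading, Section 6.7 introduces Table 12 with "When evaluating injection site reactions throughout the study, the investigator will be instructed to use the following grading scale". Table 12 makes pain Grade 2 on "Repeated use of non- narcotic pain reliever >24 hours or interferes with activity" and names no limb. It has rows for pain, tenderness, erythema and induration, and none for itching.

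Incidence and severity of local and systemic events over 7 and 28 days after each treatment is secondary endpoint 1a (Section 3.3).

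**The concern.** A severity scale has to work at every site where the product may be given. Here the functional half of two of the three anchors concerns a limb that has not been injected when the thigh is used. The half of the Mild anchor about unchanged arm use is then true however much the leg is affected, and the Moderate anchor is untrue however much it is affected.

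At stake is the raw severity record for local reactions on Days 0 to 6, which supports endpoint 1a. The subject fills the card in each evening at home. Staff review it with her 8 to 14 days after the dose, normally by phone (Sections 6.2.2, 6.2.4, 6.2.6 and 6.3.3.10). By then, what can be corrected depends on what she remembers.

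The wording looks like an oversight. The diary's own anchors for general symptoms are written in terms of usual activities. The device error form in Appendix B of the same protocol version asks whether the array was fully inserted in the arm, "or thigh as applicable", and offers both quadriceps as treatment locations.

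**Working it through.** No figure in the plan bears on this point, so the check is to apply the diary anchors literally to a thigh injection and compare the result with Table 12. The cases concern pain.

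| Reaction in the injected thigh | Mild | Moderate | Severe | Table 12 |
|---|---|---|---|---|
| (a) Little discomfort, nothing limited | Fits | Does not fit | Does not fit | Grade 1 |
| (b) More than a little discomfort, leg used less, no activity prevented | Arm half true; discomfort half not met | Arm use not reduced, so not met | Nothing prevented, so not met | Grade 2 (interferes with activity) |
| (c) A wanted or needed activity prevented | Discomfort half not met | Arm use not reduced, so not met | Fits | At least Grade 2; Grade 3 if daily activity is prevented |

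1. Case (a) is graded correctly.
2. Case (c) is captured, because the Severe anchor names no limb.
3. Case (b) is the gap. No box is literally true. The subject has to choose one that is partly wrong, and the functional wording pulls towards Mild, since her arm is unaffected. She could also mark Moderate by reading past the word arm. The documents do not settle which she would do.
4. The same three cases arise for itching, since the diary uses one set of anchors for both symptoms. Table 12 has no itching row against which the investigator could re-derive the grade.
5. For pain, the diary entry is an input and not the final grade. Section 6.3.3.10 has staff review the card and assess every reported event, and Section 7.1.5 has the investigator grade injection-site reactions on the scale that Table 12 reproduces.

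A count of affected reactions would need four quantities: the share of injections given in the thigh, the share of those with an intermediate reaction, the share of these marked Mild, and the share left uncorrected at review. The documents give none of them, so no count is offered.

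**The case against.** The strongest reply has four parts.

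**The diary does not grade by the arm alone.** A reader might infer that it does, and that any thigh pain that interferes with activity fits Mild. The text does not support this. Severe is worded by any prevented activity, and Mild also requires only a little discomfort. This stands, and it limits the gap to case (b).

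**The diary is not the severity grade.** A reader might infer that Grade 2 reactions are recorded as Grade 1 and that the site cannot re-grade them. Neither follows. The investigator grades on Table 12. The 8-to-14-day call includes an injection-site evaluation, after which staff decide whether an office visit is needed, and Section 6.6 adds site assessment at visits 2 to 4 weeks after treatment. Table 12's pain criteria can be asked about by phone, and the diary also records medications, which inform Grade 2. This largely stands for pain, except that re-grading Days 0 to 6 still depends on recall. It is weaker for itching. No grade shift can be shown for itching, because Table 12 does not grade it.

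**Thigh use is probably uncommon.** The deltoid is preferred, and the implant rule in Section 6.4 excludes only the deltoid on the affected side. This stands.

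**The current card is not visible.** The diary quoted belongs to the protocol version before 3.0. Version 3.0 still lists a participant diary card in its contents, but the text available ends before its appendices, and the error form no longer appears between the diary and the colposcopy guideline in that list. This also stands. The version 3.0 summary of significant changes mentions no diary change, which makes it plausible that the wording persists. It does not prove it, since changes classed as administrative are not listed.

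**Conclusion.** The defect holds in a limited form. In the latest diary shown, two of the three anchors for injection-site pain and itching do not apply to a permitted injection site, and a thigh reaction that reduces leg use without preventing an activity has no matching box. Such reactions may be under-graded in the diary data. That final recorded severity is in fact understated is not shown.

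The size is unknown and probably small. Both arms use the same card, so the wording gives no reason to expect a spurious difference between them, and the primary endpoint is untouched. What is exposed is the accuracy of local-reaction severity in the subset injected in the thigh, more for itching than for pain.

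The conclusion assumes that subjects read the anchors literally, that some injections are given in the thigh, and that the card in use under version 3.0 keeps this wording. Because the last cannot be checked, confidence is moderate. The change is still worth making: it costs little, and an entry made on a scale that did not fit can be repaired later only from memory.

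**What to change.** Check the diary card in use under version 3.0. If the Mild and Moderate anchors still name the arm, do one of the following on all seven diary days:

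- Replace the reference to the arm in both anchors with *the arm or leg where I was injected*.
- Reuse the activity-based anchors that the card already has for general symptoms. These name no limb and are closer to Table 12's pain criterion.

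The first keeps entries from arm injections comparable with cards already completed. The second changes the scale for every subject, so it suits a card not yet in use better. Either needs a revised card and revised translations, with no extra visit, procedure or data item.

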6.8 ASSESSMENT OF PATIENT REPORTED OUTCOMES

To assess quality of life and related impacts on subjects, previously-validated patient-reported outcomes (PRO) instruments will be provided to the subjects. PRO questionnaires will include the following, along with the license holder, respective numbers of items and domains, and listed domains:

- Short Form Health Survey, version 2 (SF-36v2[™]) (Optum, Inc.): generically measures functional health and well-being, for physical and mental health; consists of thirty-six items covering eight domains (Physical functioning, Role limitations due to physical problems, Bodily
- pain, General health, Vitality, Social functioning, Role limitations due to emotional problems, and Mental health) [24] (See Appendix D for sample questionnaire).
- EQ-5D-5L (EuroQol Research Foundation): generically measures activities & general health status; consists of six items covering six domains (Mobility, Self-care, Usual activity, Pain/discomfort, Anxiety/depression, and Global health status via VAS) [25, 26] (see Appendix E for sample questionnaire).

^{*}In addition to grading the measured local reaction at the greatest single diameter, the measurement should be recorded as a continuous variable

^{**}Induration/Swelling should be evaluated and graded using the functional scale as well as the actual measurement

The PRO instruments will be provided to subject and will be instructed to complete the questionnaire at the following time points:

- Day 0 (*before* the first study treatment)
- 8-14 days post dose 1
- 8-14 days post dose 2
- 8-14 days post dose 3
- 8 -14 days post Week 28
- 8-14 days post Week 40
- Week 88

Administration of PRO instruments will be performed according to the validated procedure and guidelines of each respective instrument, except for some assessments for exploratory analyses.

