- Moderate : I noticed the symptom. It bothered me enough that I didn't do as much as I usually do.
- Severe I really noticed the symptom. It kept me from doing something I wanted or had to do.

Day 0: Evening of Injection	on Subject#:		Date:	//	
Sometime during the evening on the refer to the time from your injection after you fill out this page but before the source of t	n to 11:59 p.m. on the	e day of injection (D	ay 0). If any of th	e items on this e information	s page changes
Temperature					
-	or °F (circle one)	Time Taken:	AM c	or PM (circle o	one)
General Symptoms If you experience any of these symtonight (Day 0). See General Inst	tructions on page 2 fo	that describes your or more information.	worst the symptom		
Symptom	None	Mild	Moderate	0.000	ere
Unusually tired/feeling unwell				_	
Muscle aches					
Headache					
Nausea					
Joint pain					
(Day 0). See General Instruction Symptom	None	Mild	Moderate		/ere
Pain					
Itching					
Redness, Swelling, or Bruising Redness	None 🗆	Provide Maximum Measurement cm at the longest part			
Swelling			cm at the longest		
Bruising			cm at the longest		
Other Symptoms If you experience symptoms other Instructions on page 2. Did you experience any other			ace below according	ig to the Gene	eral
Symnt	om or Medical Eve	ent	Mild	Moderate	Severe
Зушро	om of Medical Eve	int .			
					-
Did you take any medications If yes, please list out the name	100 VICTOR	pelow:			
-					
Participant Diary HPV-301 Version 1.0 - 10 May 2016					Page 3

203

Temperature

Take your temperature orally around the same time each evening, using the thermometer provided and record it in the space provided. Also record the time at which you took your temperature. If you recently drank very hot or cold liquids, wait 15 minutes before taking your temperature.

Injection Site Symptoms

Pain and itching

Some people experience pain in the area where they were injected. Some people may also experience itching in the area where they were injected.

• By pain we mean that the place where you were injected hurts even when it isn't touched.

If you experience pain or itching at the injection site, use the following categories to describe how severe these symptoms were. If you don't experience one or more of these symptoms, mark the **NONE** box.

- Moderate I noticed the discomfort and didn't use my arm as much as usual.
- Severe I really noticed the discomfort. It kept me from doing something I wanted or had to do.

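### The diary rounds redness and swelling up to the next circle, while Table 12 asks for a continuous diameter with a 2.5 cm floor for Grade 1; reactions just under 2.5 cm can be recorded as Grade 1

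*Protocol*

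**What the plan says.** Appendix A (Participant Diary Card, Version 1.0) tells the subject to lay the supplied tool over the injection site and "Select the circle where the longest part of the area touches the line". When the edge lies between circles the rule is "If the area is in between two circles, select the larger circle". The only circle value named in the text comes from the worked example: "the area shown to the right measures 3 centimeters (cm) because it is touching the 3cm line". Each daily page then offers an open blank, "cm at the longest part", with no printed maximum.

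Table 12 (Section 6.7) is the scale the investigator uses. By size, erythema is Grade 1 at 2.5 to 5 cm, Grade 2 at 5.1 to 10 cm and Grade 3 above 10 cm. Swelling uses the same sizes with a functional alternative: Grade 1 is "2.5-5 cm and does not interfere with activity" and Grade 2 is "5.1-10 cm or interferes with activity". The footnote on redness, printed in the supplied text under Section 6.8, adds that besides grading at the greatest single diameter "the measurement should be recorded as a continuous variable".

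The grades are used in two places. Secondary endpoint 1a (Section 3.3) is the incidence and severity of local and systemic events. Section 7.3.1 makes "Grade 3 or greater administration site erythema, and/or induration recorded" two hours or more after treatment an event for expedited reporting, and such events count towards the pausing rule in Section 7.3.2.

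**The concern.** The diary and the grading table ask for different things. Table 12 needs the actual diameter, because one of its limits, 2.5 cm, may lie between two circles and because the size is to be kept as a continuous value. The diary supplies a category, always taken upwards.

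The diary matters because it is the only scheduled size record between visits. Study staff look at the site before and about 30 minutes after each dose, and again at visits 2 to 4 weeks later (Section 6.6). The contact at 8 to 14 days is a telephone call that reviews the diary. For most of the first week, size therefore rests on what the subject wrote.

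At stake is the count of Grade 1 local reactions in endpoint 1a, and the accuracy of any summary of diameter. Erythema is the administration-site reaction that differed between arms in Phase 2b (78% against 57%, Section 2.3), so it is the one whose severity table will be read most closely. Those percentages are incidences and say nothing about size.

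**Working it through.** The plan gives no figure of its own to reproduce. The check maps true diameters to diary readings and compares the resulting grades.

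**Inputs**
- Rounding rule and the 3 cm example: Appendix A.
- Size bands: Table 12. Table 12 does not cover sizes between 5.0 and 5.1 cm; these are treated here as Grade 2.
- Circle spacing *s*: not stated. A spacing of 1 cm is inferred from the 3 cm example and from label fragments of the tool's figure, which is missing from the supplied text. A spacing of 0.5 cm is tried as an alternative.
- Circle labels are taken as diameters.

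**Formulas**
- Reading: r(d) = s × ceil(d / s), where d is the true longest diameter.
- Size grade: none if d < 2.5; Grade 1 if 2.5 ≤ d ≤ 5; Grade 2 if 5 < d ≤ 10; Grade 3 if d > 10.

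**Examples with s = 1 cm**

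| True size (cm) | Reading (cm) | Grade of true size | Grade of reading |
|---|---|---|---|
| 2.0 | 2 | none | none |
| 2.1 | 3 | none | 1 |
| 2.4 | 3 | none | 1 |
| 2.5 | 3 | 1 | 1 |
| 5.0 | 5 | 1 | 1 |
| 5.1 | 6 | 2 | 2 |
| 10 | 10 | 2 | 2 |
| 10.1 | 11 | 3 | 3 |

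With s = 0.5 cm, a 2.1 cm reaction gives 2.1 / 0.5 = 4.2, rounded up to 5, and 5 × 0.5 = 2.5 cm, which is again Grade 1.

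**All sizes from 0.01 to 15.00 cm in steps of 0.01**

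| Spacing | Ceiling | Sizes whose grade changes |
|---|---|---|
| 1 cm | none | 2.01–2.49 cm: none becomes Grade 1 |
| 0.5 cm | none | 2.01–2.49 cm: none becomes Grade 1 |
| 1 cm | 5 cm (hypothetical) | the same band; also 5.01–10 cm (Grade 2) and above 10 cm (Grade 3) both become Grade 1 |

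**Why only one limit is affected.** At 5 and 10 cm the circle lies on the limit and belongs to the lower grade. Rounding up cannot carry a size at or below 5 past 5, and a size above 5 stays above it; the same holds at 10. At 2.5 cm the limit belongs to the upper grade, so everything between the circle below and 2.5 is pushed over it.

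**Continuous value.** The overstatement is always less than one spacing. With 1 cm circles, a 2.1 cm reaction written as 3 cm is too large by 3 − 2.1 = 0.9 cm.

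**The case against.** The best defence has four parts.

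First, the investigator grades, not the diary. Staff review diary entries for clinical significance, subjects are told to report events at once, and the 8 to 14 day call can lead to an office visit. The continuous-variable footnote is addressed to the investigator's scale. This is fair, but none of it supplies another scheduled size measurement between visits, so a grade for those days will usually start from the rounded number.

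Second, the spacing is not stated. That stands. The direction of the error follows from the text; its extent depends on the spacing. A finer tool would narrow the affected band.

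Third, the rule is the same in both arms of a blinded trial, and it over-reports rather than conceals. That also stands and is a main reason to rate the point low.

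Fourth, the diary and Table 12 quoted here belong to the text before version 3.0. The supplied version 3.0 text stops in Section 6.1.1, before its Sections 6.7 and 7.3.1 and its Appendix A. Its summary of changes lists no diary change and renames the expedited events as adverse events of special interest, but its diary and grading table cannot be checked.

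A reader might go further and infer that the tool ends at 5 cm, so that Grade 2 and 3 redness or swelling cannot be recorded. The documents do not support this. The idea rests on label fragments of a missing figure, the figure serves as an example, the tool is a separate item whose range is never given, and the entry blank has no maximum. Swelling can also reach Grade 2 or 3 on function. Erythema has no functional route, so the tool's range is worth asking about.

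**Conclusion.** The diary's rounding rule contradicts Table 12 and its footnote. With circles at 1 cm or 0.5 cm, reactions of 2.01 to 2.49 cm move from ungraded to Grade 1, and the recorded diameter is too large by anything up to one spacing. Without a ceiling, no Grade 2 or Grade 3 reaction is misgraded by size, so neither the Grade 3 reporting trigger nor the pausing rule is shown to be affected.

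The result assumes that circle labels are diameters, that the spacing is one of the two tried, and that the version 3.0 diary keeps the rule. The share of subjects affected cannot be stated: no document gives a distribution of reaction size, and any percentage would reflect an invented one. Severity is low. The point is worth correcting because it bears on secondary endpoint 1a and the correction is cheap.

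**What to change.** In the diary, delete the instruction to take the larger circle and have the subject write the actual longest diameter, in cm to one decimal or in mm. The existing blank can hold it. The investigator then grades from that number with Table 12, as the protocol already provides; no change in who grades is needed.

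Ask the sponsor to state the spacing and largest marking of the supplied tool, and to confirm that it marks 2.5 cm and extends past 10 cm. Make the same check on the version 3.0 diary and grading table.

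The cost is one diary revision and brief retraining of subjects. If some subjects have already used the rounded diary, summaries should note which diary version each reading came from.
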